5.1. Inclusion Criteria

Subjects who meet all of the following criteria will be eligible for the study:

- ≥ 12 years of age and ≤ 18
- Scheduled for a new patient clinic visit at the multi-component PWM program at CCHMC or HDVCH
- Severe obesity ($\geq 120\%$ of the 95th percentile for BMI based on age and gender at time of screening visit)
- Able to understand and complete the consent process
- Have access to a smart phone, device, or computer with a web camera
- Have access to the internet

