6. STUDY PROCEDURES

Screening Visit— Adolescents and their parents/guardians who appear to qualify for the study based on the telephone interview will be scheduled to attend a screening visit. At the screening visit, height and weight measurements for the adolescent will be obtained by a qualified member of the study staff, using a standardized protocol and demographic information (date of birth, sex, race, ethnicity, and type of health insurance coverage) will be obtained and recorded. Adolescents and their parents/guardians who meet all inclusion/exclusion criteria, and express interest in participating in the study, will engage with a qualified member of the study staff who will review the consent/assent with the participant and their parent/guardian to ensure information presented is understood prior to obtaining the appropriate signatures for the IRB-approved informed consent/assent form. At the screening visit, participants and their parents/guardians who have met all criteria and informed consent/assent was obtained, will be enrolled in the study. Enrolled subjects at the screening visit will then be randomly assigned to either the *Intervention* or *Control* group, using a 2 *Intervention*:1 *Control* randomization ratio. At the end of the screening visit, all participants will be given a reminder card about their scheduled initial medical assessment visit with the PWM program. The week prior to this clinic visit, they will also receive a reminder call. This initial medical visit with the PWM program will serve as the baseline assessment visit for the study.

Group Assignment – Subjects will be randomized to either the Intervention or Control group using a 2 *Intervention*:1 *Control* randomization ratio. The randomization plan will be stratified by study site such that the 2:1 randomization ratio will be obtained within each study site. In addition, randomization will be stratified by baseline obesity status (Class 2, Class 3) to ensure the appropriate balance of obesity classes within each treatment group. A statistician independent from the study team will provide the

randomization plan so that the study team is blinded to the group assignment for each newly enrolled patient until that patient is randomized.

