Program Orientation – Immediately after the screening visit, participants assigned to the *Intervention* group will attend an individual Program Orientation session. This will include the following: 1) Detailed site-specific description of the PWM program; 2) Assessment of “readiness to change” and barriers to lifestyle changes using motivational interviewing strategies, including “confidence rulers”; 3) Completion of selected validated mental health assessment questionnaires; and 4) Scheduling of FIEs between clinic visits. The frequency, time spent, and type of FIE will take into consideration the needs of each patient-family enrolled in the study. The adolescent and parent/guardian will determine whether they will participate together during a FIE, do them separately or have a combination of the two. The frequency of contact between clinic visits will be determined by the number of contact hours provided by clinic visits as part of the “standard-of-care” over a 6-month treatment. The goal for the *Intervention* group is to have a total of 26 provider contact hours over the 6-month treatment period. After accounting for the contact hours from clinic visits as part of the “standard of care”, the balance of the 26 contact hours will consist of FIEs scheduled between clinic visits. At the end of the Program Orientation, the subject and parent/guardian will schedule FIEs and use tracking calendar booklet provided to keep record of their scheduled clinic visits and FIEs for the first month of treatment. A summary of the findings from the mental health assessment measures, assessment of “readiness to change” and barriers to lifestyle change for each subject in the *Intervention* group will be reviewed with the clinical team at each site prior to the initial medical visit with PWM program (Table 1). **Baseline Assessment** - Each participant (*Intervention and Control groups*) will complete at their initial medical visit with the PWM program a baseline assessment that includes the following measures: 1) Anthropometric measurements (height and weight); 2) Body composition assessment (% body fat, skeletal muscle mass, fat-free mass); and 3) Blood pressure (systolic and diastolic). Fasting blood work (plasma lipids, glucose, liver enzymes, and hemoglobinA1c) will be obtained up to 3 months prior to the initial medical visit or up to 6 weeks after the initial medical assessment visit. Fasting blood samples will be drawn for the laboratory analyses by qualified staff at a certified medical laboratory affiliated with CCHMC and HDVCH. Standardized methods and analytic procedures will be done for each blood parameter. The results of all clinical measurements and laboratory values, and referrals and/or additional clinic visits made to address mental health concerns will be recorded on the study’s source document, specific for each subject. In addition contact time and provider types involved in the initial medical visit will also be recorded (Table 1).

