6.1. Process of Obtaining Informed Consent

A waiver of documentation of consent will be in place to collect patient height and weight to determine subject eligibility prior to the patient being consented. Consent, parental permission and/or assent will be obtained from all patients before any other study related procedures are performed. Written assent will be obtained from participants 12 years of age and older. The investigator will be available to answer any questions that the participant or parent may have regarding procedures, risks and alternatives. The consent process will be documented on the informed consent progress note. A copy of the signed consent(s) will be kept in the patient's medical record.

The study team will monitor the age of each participant. If a participant turns 18 during their study participation, the investigator or study coordinator will approach the participant during a routine clinic visit to confirm they would like to continue their participation in the study. The participant will be asked to sign a fresh consent form, documenting their consent.

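### Aim 4 takes its weight baseline after randomisation and the Intervention-only orientation, although a pre-randomisation value is already collected; late baseline laboratory draws need timing reports by arm

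*Combined protocol and SAP*

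**What the plan says.** **Order of events (section 6).** At the screening visit "height and weight measurements for the adolescent will be obtained by a qualified member of the study staff". Section 6.1 provides a waiver "to collect patient height and weight to determine subject eligibility prior to the patient being consented", so these values precede consent. Section 5.1 judges severe obesity on them ("based on age and gender at time of screening visit"). Randomisation follows at the same visit: "Enrolled subjects at the screening visit will then be randomly assigned to either the" Intervention or the Control group. It is stratified by site and by obesity class (2 or 3), and the plan calls that class a baseline status.

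Orientation comes next, for one arm only: "Immediately after the screening visit, participants assigned to the" Intervention group attend it. Primary Aim 1 (section 3) requires this attendance to come before the initial medical visit, and section 6 has the clinical team review the orientation findings before that visit. Only then comes the study baseline: "This initial medical visit with the PWM program will serve as the baseline assessment visit for the study".

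**Analysis (section 8.1, Aim 4).** The dependent variable for every health outcome is change from baseline, and the baseline value is an optional covariate. The section does not define baseline by outcome and does not mention the screening height and weight.

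**Laboratory samples.** Baseline fasting blood work "will be obtained up to 3 months prior to the initial medical visit or up to 6 weeks after the initial medical assessment visit". Section 8.1 analyses the change to 6 months. It does not say how draw dates are reported or examined. Remote encounters (FIEs) for the first month are arranged for the Intervention arm only.

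**The concern.** The word baseline has two meanings. For stratification it can only be the screening measurement, because randomisation happens at that visit. For Aim 4 it is a later measurement, taken after randomisation and after one component of the intervention package. If orientation, which includes motivational interviewing, changes weight before the initial visit, that part of the treatment effect moves into the baseline and out of the contrast.

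For laboratory outcomes, a sample drawn after the initial visit may follow contacts that only the Intervention arm receives. Without draw dates by arm, a reader cannot tell whether this matters or in which direction.

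The stake is modest but real. Aim 4 is secondary and section 8.2 rules out confirmatory testing, but the Preliminary Studies text says the pilot's treatment-effect estimates will help design the full trial.

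**Working it through.** **1. Which baselines can arm-specific contact have touched?**

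| Measurement | Relative to randomisation | After orientation (Intervention)? |
|---|---|---|
| Screening height and weight | Before | No |
| Initial-visit weight, body composition, blood pressure | After | Yes |
| Lab draw before screening | Before | No |
| Lab draw between randomisation and initial visit | After | Yes |
| Lab draw up to 6 weeks after initial visit | After | Yes, and FIEs may have begun |

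The Schedule of Procedures shows no body composition, blood pressure or blood work at screening, so a pre-randomisation study value is assured only for weight status.

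**2. What the weight contrast loses.** Let T be the between-arm effect on the 6-month value, e the between-arm effect already present at the initial visit, and b the within-arm slope of the 6-month value on the initial-visit value.
- Unadjusted change from the initial visit estimates T − e.
- The same change adjusted for the initial-visit value estimates T − b·e.
- Change from screening, adjusted or not, estimates T, because randomisation balances the screening value in expectation.

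The documents give neither e, nor b, nor the gap from screening to the initial visit. Section 5 says only that candidates are scheduled at least 4 weeks ahead.

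**3. Scale for weight (illustration only).** The two sites' 6-month change has an IQR of −4 to 3 (Preliminary Studies). If normal, SD = 7/1.349 = 5.19 points. This is rough: the median, −1.7, is off the IQR midpoint of −0.5.
- 40/20: SE = 5.19 × √(1/40 + 1/20) = 5.19 × 0.274 = 1.42 points.
- 30/15 (also in Table 3): SE = 5.19 × √(1/30 + 1/15) = 1.64 points.

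An assumed e of 0.2, 0.5 or 1.0 point is 0.14, 0.35 or 0.70 SE at 40/20. An e of 0.5 is 0.30 SE at 30/15.

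**4. Unit of Table 3.** The table states no unit. For 40/20, 80% power and two-sided 0.05, a two-sample t calculation in SD units gives 0.780, which rounds to the printed 0.8. All 12 cells match to one decimal on this reading, so SD units are used below (SD 1, SE 0.274 at 40/20).

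**5. Late lab draws, same timing in both arms.** Under linear accrual over 26 weeks, a draw at week w loses w/26 of that participant's effect: 3/26 = 12% and 6/26 = 23%. With the 6-month visit at week 24 or 30 (its −2/+4 week window), a week-6 draw loses 25% or 20%. Under front-loaded accrual with half-life h, the loss is (1 − 2^(−w/h))/(1 − 2^(−26/h)). For w = 6 that is 37% (h = 13) or 53% (h = 6); for w = 3 and h = 6 it is 31%. Overall loss = share drawn late × loss per late draw. The shares are assumed:

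| Share late (weeks 3 to 6) | Linear | Half-life 6 weeks |
|---|---|---|
| 10% | 1–2% | 3–5% |
| 25% | 3–6% | 8–13% |
| 50% | 6–12% | 15–26% |

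In the largest linear case (50% at week 6), an effect of 0.5 to 0.8 SD loses 0.06 to 0.09 SD, or 0.21 to 0.34 SE.

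**6. Late lab draws, timing different by arm.** Let d be the effect, g the Control gain, f = 6/26, and sI and sC the late shares in Intervention and Control. The contrast is (g + d)(1 − sI·f) − g(1 − sC·f), so bias = −d·sI·f + g·f·(sC − sI). With d = 0.50 and g from 0.2 to 0.5:
- 50% late in Control only: 0.52 to 0.56 (too large).
- 50% late in Intervention only: 0.42 down to 0.385 (too small).

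**7. Keep or drop late samples?** Root mean squared error for d = 0.5, week-6 draws, linear accrual, same timing in both arms, keeping all versus dropping late draws: 0.274 vs 0.289 (10% late), 0.275 vs 0.316 (25%), 0.280 vs 0.387 (50%). With the 6-week half-life, d = 0.8 and 50% late: 0.345 vs 0.387. Keeping all samples was better in every case tried.

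**The case against.** **Programme entry is a legitimate starting point.** The plan names the initial visit as baseline for both arms, and the registry figures also start at the clinic visit. This stands as a reason to keep reporting change from that visit. It does not make that visit a pre-treatment baseline for the randomised contrast, because orientation is part of the package under test.

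**The weight effect is probably small.** Orientation is a single session of description, assessment and scheduling. This stands. A reader might infer that the Aim 4 weight result is materially biased, or that the early effect is always lost in full. The documents support neither: no early effect is given, and full removal is exact only for an unadjusted change score.

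**A screening baseline has its own costs.** It adds a variable pre-programme gap and perhaps some noise, and it puts weight on a different clock from body composition and blood pressure. Screening values are taken by study staff, whereas the Height paragraph assigns clinical staff. These points stand, which is why the choice of main analysis should depend on whether measurement matches. The precision cost cannot be computed from the documents. Because screening BMI decides eligibility, within-arm change may include regression to the mean, but this does not bias the arm contrast.

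**The laboratory window is itself a rule.** It settles which samples count as baseline, and section 8.1 analyses them. This stands. A reader might infer that late draws make the main laboratory analysis wrong, that they always pull the estimate toward zero, or that they should be excluded. Steps 6 and 7 do not support any of these. What is missing is a report of draw timing and a sensitivity analysis.

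**Conclusion.** The weight point holds as a minor, cheap improvement. The order of events is plain in the text: the Aim 4 weight baseline follows randomisation and one Intervention-only component, while an untouched value is collected and already used for stratification. The bias cannot be derived and is probably small; the standard-error figures rest on assumed effects, approximate normality and complete arms.

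The laboratory point is secondary and concerns reporting. Late draws are permitted, not required, in both arms. With similar timing they dilute the contrast, by 23% of the effect for each participant drawn at week 6 under linear accrual. With unequal timing the bias can go either way. Late shares, accrual shape and Control gain are all assumptions.

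**What to change.** **Weight.** In section 8.1, define baseline for each outcome. Prespecify a between-arm BMI analysis in all randomised participants with the screening percent of the 95th percentile as both baseline and covariate, and report it beside change from the initial visit, which is kept for comparison with the registry. Make the screening-based analysis the main one if screening uses the procedure and equipment of the Height and Body Weight paragraphs; otherwise make it the sensitivity analysis. Body composition and blood pressure keep the initial-visit baseline.

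**Laboratory measures.** Keep every sample in the main analysis. Record each draw date relative to randomisation and to the initial visit, and report the number and timing of late draws by arm. Add a sensitivity analysis limited to samples drawn on or before the initial visit, and show separately those drawn before randomisation, because draws between randomisation and the visit follow orientation in the Intervention arm. This set is smaller and selected on a post-randomisation event, so it is supportive only.

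**Cost.** SAP wording and one draw date per sample, which the source document may already hold. No new measurement or visit is needed. The price is two baseline times within Aim 4 and the screening-baseline drawbacks set out above.

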6.1. Process of Obtaining Informed Consent

A waiver of documentation of consent will be in place to collect patient height and weight to determine subject eligibility prior to the patient being consented. Consent, parental permission and/or assent will be obtained from all patients before any other study related procedures are performed. Written assent will be obtained from participants 12 years of age and older. The investigator will be available to answer any questions that the participant or parent may have regarding procedures, risks and alternatives. The consent process will be documented on the informed consent progress note. A copy of the signed consent(s) will be kept in the patient's medical record.

The study team will monitor the age of each participant. If a participant turns 18 during their study participation, the investigator or study coordinator will approach the participant during a routine clinic visit to confirm they would like to continue their participation in the study. The participant will be asked to sign a fresh consent form, documenting their consent.

7. DATA COLLECTION AND MANAGEMENT

7.1. Data Management

The Data Management Center (DMC) at CCHMC will provide full data management support to the project. The DMC will develop the data capture system using a web-based data collection system, REDCap, as the primary source of data entry and storage. Data will be recorded on study specific case report forms (CRFs) and entered into the REDCap data base. Some data may be entered directly into the REDCap data base from source documents. Participants will be given a study identification number that will be reported on all CRFs. REDCap is a software toolset and workflow methodology for electronic collection and management of research and clinical trial data developed by Vanderbilt University, with collaboration from a consortium of institutional partners including the University of Cincinnati, Academic Health Center. The DMC will develop, test and maintain the REDCap data entry system, the data management plan, data quality checks and query management, and preparation of the data for analysis.

The REDCap system provides a secure, web-based application that is flexible and provides: 1) an intuitive interface for users to enter data and have real time validation rules (with automated data type and range checks) at the time of entry; 2) HIPAA-compliant and 21 CFR Part 11-ready audit trails for tracking page views, data manipulation and export procedures; 3) record locking and electronic signature functions; 4) fine grained control of user rights to view and manipulate data, and tool to sequester data access for multiple sites; 5) a report builder for reporting, monitoring and querying patient records; and 6) automated export procedures for seamless data downloads to common statistical packages (SPSS, SAS, Stata, R/S-Plus).

REDCap is hosted on a network specially designed to support the rigorous security and compliance requirements of basic, clinical and translational research projects. Administered by the Division of Biomedical Informatics (BMI), this network features

multiple firewalls as well as a central facility for managing hosted systems and users. The result is another layer of access control and audit capability on top of what REDCap already provides. For example, a user's ability to access a REDCap study or even a specific questionnaire can be monitored and controlled at the network level without making any changes within REDCap itself. These capabilities are available to authorized BMI network administrators and REDCap study owners only, and all user access changes are documented by an automatic audit trail.

8. DATA ANALYSIS

8.1. Study Endpoints

Demographic and clinical characteristics will be summarized overall and within each center using frequency and percent for categorical data and median and interquartile range for the continuous measurements. For each aim below, the two-sided 95% confidence intervals will be calculated using the Score Confidence Interval.³⁴ All comparisons between the intervention and control groups will be tested at the two-sided, 5% level of significance.

Aim 1: For patients in the intervention group only, percentages and two-sided 95% confidence intervals will be presented for the each of the components of the “Bundle of Program enhancements (BPE)”: a) percent of participants attending the program orientation; b) percent of participants completing each of the mental health questionnaires; 3) percent of participants completing the “readiness to change” clinical assessment; 4) percentage of participants that complete scheduling of interactive encounters (FIE) between clinic visits for 1st month of treatment; and 5) Percent of participants that complete scheduling of FIE between clinical visits for each of months 2-6 of treatment. Each confidence interval will be examined to determine if the hypothesized value of 80% is contained within the interval.

Aim 2: For patients in the intervention group only, the percentages and two-sided 95% confidence intervals will be calculated for the intervention group only for the percent of patients that complete at least 26 contact hours during the 6-month treatment period. The confidence interval will be examined to determine if the hypothesized value of 70% is contained within the interval. In addition, the mean and 95% confidence interval will be presented for the percent of FIE completed by each patient and also for the total number of contact hours completed by each patient. These measures will also be provided for the subset of patients in the intervention group that are identified with mental health problems and descriptively compared to the subset of patients in the intervention group without mental health problems.

Aim 3: The rate of participation in on-site scheduled visits (i.e. clinic visits, group sessions) will be calculated for each patient in both the intervention group and the control group as the percentage of all scheduled visits during the 6-month period that was attended by the patient. These percentages will be compared between groups using the mixed effects model with treatment as a factor and site as a random effect. Additional covariates in the model may include baseline weight status as measured by percent of the 95th percentile, sex, race, ethnicity, socioeconomic status, and distance from clinic site. To the extent possible, interactions of covariates with treatment group will be examined and discussed if significant at $p<0.10$ level of significance.

Transformations will be used (e.g. arcsin square root, log, rank) if needed to satisfy the assumptions of the model. The percentage of patients that complete the 6-month program will be analyzed using the same approach discussed above. In addition to doing hypothesis testing, treatment differences (unadjusted and also adjusted for covariates) and 95% confidence intervals will be presented.

Aim 4: Health outcomes measured by weight status, body composition, and blood pressure will be compared between the intervention and control groups using the repeated measures mixed effects analysis with center as a random effect. The outcome metric for weight status in the proposed study will be the change in percent of the 95th percentile for BMI (based on age and sex).

For each outcome, change from baseline will be calculated and included as the dependent variable. Terms in the model will include treatment, month (i.e. 3, 6 month) and the interaction of treatment by month. If the interaction is not significant at the two-sided $p<0.10$ level, it will be removed from the model. Appropriate contrasts will be used to compare the treatment groups at 3 months and at 6 months. Covariates in the model may be the same as those listed in Aim 3. The respective baseline measure may also be included as a covariate in the model for each health outcome. Laboratory measures will be measured at baseline and at 6 months of treatment. The mixed effects model using change in laboratory measure as the dependent variable and treatment as independent variable and center as random effect will be used. Covariates may include those listed for Aim 3 and the respective baseline laboratory measure.

